#### Training Program

The exercise training sessions will include 5 minute warm up, 5 minute cool down (at the end) and a combination of aerobic and resistance exercises. In weeks 1 and 2 aerobic exercises will be performed for 15-20 minutes and will include the utilization of an ergometer (e.g., stationary bicycle, treadmill, Stairmaster and rowing machine) and or playing small group games, stationary punching bag and adapted ball games (e.g., basketball, soccer, badminton). The duration of the aerobic exercises will be gradually increased and will get up to 45 minutes by weeks 8-10. In addition to the aerobic exercises, participants will be performing resistance exercises (e.g., light free weights, band exercises, pushups, and pull-ups). These exercises will be done in sets, starting from low number (4-6) of repetition within each set, and will gradually increase to 10-12 repetition in a set. The number of sets will also be gradually increased based on the participant strength. Resistance exercises will take approximately 20-25 minutes in the first few weeks and gradually decrease in time in parallel to the increase in time for the aerobic exercises. Each training session will last approximately an hour.

#### **Collecting saliva to measure stress and inflammatory mediators:**

Weeks one, in the middle of the training program and the last week of training

The hypothalamic-pituitary-adrenal (HPA) axis is a major homeostatic system which under basal conditions maintains a circadian rhythm and is activated in response to stress. Measurement of salivary cortisol has provided a great deal of experimental information on activity of the HPA axis in health and disease and on the involvement of cortisol in the mechanisms determining our reactivity and adaptation to environmental changes. A relatively noninvasive technique, salivary sampling has the dual advantage over blood sampling of (i) permitting cortisol to be measured without contamination of results by needle stress, and (ii) extending investigation beyond experimental laboratory studies through the ease of home sampling (4).

Saliva will be collected 3 times a day (3 samples) over two consecutive days (total of 6 samples). Two baseline values followed by one additional sample of salivary collections: T0-In bed: when waking up before brushing teeth, T2, 30 min after waking up and before brushing teeth, and T3-before dinner. This will be repeated the following day. Saliva collection kits will be sent home. Parents/guardians will assist their children to collect the samples.

We will also collect saliva before and after the exercise challenges that will be performed at PERC/ICTS Performance Lab, at the beginning and the end of the program.

### **Assessment of physical activity over 7 days:**

This will occur during week one, in the middle of the training program and in the last week of training program.

Actigraph assesses movements resulting from muscle force as well as accelerations due to changes in the position of the sensor in the gravitational field (5). Actigraphy has become a valuable clinical and research tool to objectively evaluate sleep, daytime activity, and circadian activity rhythms in health and disease (6, 7).

Actigraphs will be given by the trainers in the training session at the beginning, middle and the end of exercise program. After the training session, subjects will take the ActiGraphs home and put them on for 7 days. Actigraphs are worn on the waist with an elastic band. Subjects /parents will be asked to fill activity diaries for each of the seven days, recording the time they woke up, the time they went to bed, and time they removed the actigraph. As well as major activity events during the day (e.g., PE in school, soccer, taking a walk, biking, etc.)

### **Assessment of exercise intensity during an exercise session**

Heart rate monitors (watches worn on the wrist) will be used by the trainers during the training sessions to assess exercise intensity.

### **Executive Function assessment**

Executive Function assessment will be done using Hearts & Flowers tasks (Adele Diamond Laboratory, 8, 9). These executive function tasks are administered via touch-screen computers and will require 5 minutes per participant. See <http://www.devcogneuro.com/eftasks.html> for detailed descriptions of tasks. [name] will supervise the assessment before, in the middle and after the training program.

### **Using the Blood Donor Program**

In order to set up the leukocyte genomic and functional assays and for cell culture experiments that are looking at the leukocyte genomic and functional response to various stimuli, we will use human whole blood from healthy individuals that will be drawn by ICTS nurses as part of the UCI ICTS Blood Donor Program. No code linking back to identifiers will be created or accessed.

**Table 1. Study Overview—Timeline, Measures, Activities, and Outcome Variables**

Time	Measure/Activity	Description
Weeks 1		
PERC/ICTS Lab: Fitness Assessment (Approximately 2 hours)	Clinical Assessment	
 
• Clinical History of Asthma
 
• Asthma questionnaire
 
• Vitals and anthropometric measures (blood pressure, temperature, height and weight)
 
• Pubertal stage (by questionnaire), and pregnancy test for eligible females.
 

	Progressive Exercise Testing	
 
• Ramp type protocol to assess peak VO2 (aerobic fitness)
 
• Pre- and post-exercise Exhaled NO measurements
 
• Pre- and post-exercise PFTs
 
• Pre- and post-exercise blood flow measurements
 
• Pre- and post-exercise saliva collection
 

	DXA	
 
• Body composition (lean and fat mass)
 

	Executive Function Test	
 
• Executive function tasks – 5 min of specific computer games
 

PERC/ICTS Lab: Exercise Challenge (separate at least 48 hours from the Fitness Assessment visit) (Approximately 3 hours)	Exercise Challenge on a cycle ergometer (10 x 2-min bouts @ ~70% peak work rate, with 1-min intervals)	
 
• Blood draw* (before, immediately after, and one-hour after the exercise challenge).
 
• Pre- and post-exercise Exhaled NO measurements
 
• Pre- and post-exercise PFTs
 
• Pre- and post-exercise saliva collection
 

PERC/ICTS Lab: Exercise Challenge (Approximately 2 hours)	Exercise Challenge on a cycle ergometer (10 x 2-min bouts @ ~70% peak work rate, with 1-min intervals)	
 
• Pre- and post-exercise blood flow measurements
 
• Pre- and post-exercise PFTs
 

At Home	Nutritional Assessment	24-h food recalls over 3 days
Week 2		
At Home	Actigraph	
 
• Assessment of physical activity over 7 days
 

		
 
•
 

At Home	Saliva Collection	
 
• 3 times a day (3 samples) over two consecutive days
 

Weeks 2-11		
In the Field (Approximately 1 hour per session for up to 30 sessions)	Exercise-Training	
 
• Personal trainers, small-groups, community venues, tailored training sessions x 3 weekly
 

	Compliance	
 
Attendance at exercise sessions
 
Exercise intensity will be assessed using heart rate (HR) monitors
 

Week 6-7		
At Home	Actigraph	
 
Assessment of physical activity over 7 days
 

At Home	Saliva Collection	
 
3 times a day (3 samples) over two consecutive days
 

Week 11		
At Home	Actigraph	Assessment of physical activity over 7 days
At Home	Saliva Collection	3 times a day (3 samples) over two consecutive days
Weeks 12		
PERC/ICTS Lab: Fitness Assessment (Approximately 2 hours)	Clinical Assessment	
 
Clinical Evaluation
 
Vitals and anthropometric measures (blood pressure, temperature, height and weight)
 

	Progressive Exercise Testing	
 
Ramp type protocol to assess peak VO2 (aerobic fitness)
 
Pre- and post-exercise Exhaled NO measurements
 
Pre- and post-exercise PFTs
 
Pre- and post-exercise blood flow measurements
 
Pre- and post-exercise saliva collection
 

	DXA	
 
Body composition (lean and fat mass)
 

	Executive Function Test	
 
Executive function tasks – 5 min of specific computer games
 

PERC/ICTS Lab: Exercise Challenge (separate at least 48 hours from the Fitness Assessment visit) (Approximately 3 hours)	Exercise Challenge on a cycle ergometer (10 x 2-min bouts @ ~70% peak work rate, with 1-min intervals)	
 
Blood draw* (before, immediately after, and one-hour after the exercise challenge).
 
Pre- and post-exercise Exhaled NO measurements
 
Pre- and post-exercise PFTs
 
Pre- and post-exercise saliva collection
 

PERC/ICTS Lab: Exercise Challenge (Approximately 2 hours)	Exercise Challenge on a cycle ergometer (10 x 2-min bouts @ ~70% peak work rate, with 1-min intervals)	
 
Pre- and post-exercise blood flow measurements
 
Pre- and post-exercise PFTs
 

		
 

 

At Home	Nutritional Assessment	
 
24-h food recalls over 3 days
 

		
 

 

\*Primary Outcome Variable: Gene expression in Leukocytes

## B. Statistical Analysis Plan

1. **Variables of Interest** - Clearly identify the primary outcome(s) and key factor(s) of interest.
2. **Statistical goal** - State the statistical goal(s) of the study (e.g., Comparison of group means, estimation of the proportion of success, estimation of variability for future study design, etc.).
3. **Statistical approach** - Describe the statistical approach(es) to be used to address the study's statistical goal(s) (e.g., T-test to compare means, confidence interval estimate(s), etc.). *Note: Required for ICTS SRC review.*
4. **Secondary analyses** - Clearly state any secondary analyses to be performed including secondary outcomes and comparison groups along with the statistical methods that will be used to perform the secondary analyses. *Note: Required for ICTS SRC review.*

***If a statistical analysis plan is not appropriate for your study design, please describe a non-statistical plan for assessing your study results.***

***Aim 1: Elucidate key abnormal genomic and epigenetic responses to brief exercise in leukocytes of children and adults with moderate-to-severe asthma.***

***Aim 2: Identify the effect of training on the key genomic and epigenetic exercise response mechanisms in leukocytes in children and adults with moderate-to-severe asthma.***

Genomic expression profile is the **primary outcome variable** for Aims 1 and 2. Gene expression data will be normalized, log-transformed, and quality-checked and filtered across all arrays from all study subjects. Pre- to end-exercise change and before- to after-training change will be calculated for each subject and each probe set. Probe sets that pass filtration and belong to

selected functional pathways will be examined for group difference using 2-sample t-test and further adjusted with false discovery rate (FDR) controlling adjustments as described by Benjamini and Hochberg.

Leukocyte cell-function profile is the **secondary outcome variable** for Aims 1 and 2. Each outcome variable will be treated as an individual hypothesis. The primary analysis will apply 2-sample t-test to examine group difference in exercise effect and in training effect. The secondary analysis will utilize mixed model to evaluate group difference in training and exercise effect together, adjusting for possible confounding factors such as gender, BMI percentile, and fitness level.

**Aim 3:** *Assess the clinical impact of exercise training in children and adults with persistent asthma on: (a) exercise induced airway inflammation, (b) asthma control, and (c) cardiorespiratory fitness and muscle adaptation.*

Outcomes from Aim 3 are considered as secondary outcome variables. We will apply paired t-tests for before- to after-training change. Furthermore, we will employ linear regression model to examine the effect of covariates such as gender, asthma severity (ACQ), and lean muscle tissue response to exercise-training (as determined by DXA).

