#### **SECTION 4: SUBJECTS (PERSONS/CHARTS/RECORDS/SPECIMENS)**

##### **A. Number of Subjects (Charts/Records/Biospecimens)**

1. Indicate the **maximum number of subjects to be recruited/consented** on this UCI protocol. This is the number of potential subjects you may need to recruit to obtain your target sample size. This number should include projected **screen failures and early withdrawals**. *Note: The IRB considers individuals who sign the consent form to be "enrolled" in the research.*
2. For **Mail/Internet surveys** include the number of people directly solicited.
3. If the study involves use of **existing charts, records, biospecimens**, specify the maximum number that will be reviewed/tested to compile the data or the sample population necessary to address the research question.

The maximum number of subjects to be recruited/consented on this protocol is 240. This number includes screen failure and early withdrawals (see table 2 for breakdown in subjects for each group).

4. Of the maximum number of subjects listed above, indicate the **target sample size** for the study. This is the number of subjects expected to complete the study or the number necessary to address the research question.
5. For *social/behavioral research*, the maximum sample size is often similar to the target sample size. If the **maximum sample size** is significantly greater (i.e.,  $\geq 1.5x$ ) than the **target sample size** provide a justification.
6. For studies where multiple groups of subjects will be evaluated, **provide a breakdown per group** (e.g. controls vs. experimental subjects; children vs. adults; by age group).

Of the maximum number of participants, our target sample size is 200. Below is a table with a breakdown in the number of participants per group.

Table 2: Subject number break down per group for maximum number to be recruited and target number of participants.

	Maximum to be Recruited		Target Participants	
	Control	Asthma	Control	Asthma
Mid and late pubertal boys (Tanner 3-5) age 8 - 17 years	35	35	30	30
Mid and late pubertal girls (Tanner 3-5) age 8 - 17 years	35	35	30	30
Young adult women aged 18-35	25	25	20	20
young adult men aged 18-35	25	25	20	20
Total number of subjects	240		200	

7. For **multi-center research**, indicate the overall sample size for the entire study (across all sites).

Not applicable - This study is not a multi-center research study.

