8. Explain **how the overall target sample size was determined** (e.g., power analysis; precision estimation).

9. Demonstrate that the **target sample size will be sufficient** to achieve the study goal and should coincide with the statistical approach **described in Section 3B**.

10. **Sources and information** of assumed group effects and variability should be supplied (e.g., pilot data; data from related literature).

To accomplish our aims, we will recruit 70 asthmatics and 70 gender-, age- and fitness-matched controls (as noted, below the 50th percentile of appropriate normative data) to participate in the training course. Given an anticipated dropout rate (based on our experience in recruiting subjects in this region) of about 10-15%, we expect to have complete samples around 60 participants in each group of children. The power analyses were based on PASS 2008 (Hintze, J. (2008). NCSS, LLC. Kaysville, Utah. [www.ncss.com](http://www.ncss.com)).

For the adult groups we will recruit 50 asthmatics and 50 gender, age and fitness-matched controls. We expect to have complete samples around 40 participants in each group.

For the primary outcome in gene expression, we will include about 3000 probe sets belonging to functional pathways of interest in asthma and exercise, as described above and in the Preliminary Studies Section. After filtration, around 1000 to 2000 probe sets will be left for analysis. Table 3 in the Human Subjects Section shows the power and effect size that can be detected from microarray data using a 2-sided 2-sample t-test for a range of: (1) probe sets **to examine** and (2) significant probe sets **to detect** (with FDR at 0.05 level). With the same power, a smaller effect size can be detected with a larger sample size. Effect size is defined as the expected log-transformed group difference divided by the within-group standard deviation. Our previous data showed that about 5% of the probe sets have an effect size over 0.9.

Table 4 shows the power analysis for the secondary outcome variables (e.g., in Aim 1, leukocyte function; in Aim 2, change in exhaled NO after the exercise challenge). The effect size is defined as the expected group difference divided by the within-group standard deviation for 2-sample t-test and as the mean difference between before- and after-training divided by the standard deviation of the difference for paired t-test.

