## B. Inclusion and Exclusion Criteria

1. Describe the **characteristics and provide justification** for inclusion of the proposed subject population. At a minimum include information about the age and gender of the study population.
2. Describe **different subject groups** (e.g., students and teachers; control group and treatment group(s), children and adults) separately.

The study population will consist of 60 children with Asthma (boys and girls, 8-17y/o) and 40 adults with Asthma (men and women, 18 yrs -35y/o) who: have been determined to be in good health by pre-participation sports physical performed at PERC, have no evidence of disease or disability that would impair participation in a vigorous physical activity program, have been diagnosed with persistent asthma according to criteria by NHLBI, have a clinical history of suggestive of exercise induced bronchoconstriction, have less than 50% fitness as determined from our own normative data collected in our lab (N=95), and with BMI percentile < 95th.

The control groups will be age, gender, and fitness matched with asthmatic participants, and consist of 60 children (boys and girls, 8-17yrs) and 40 adults (men and women, 18yrs -35y/o) who have been determined to be in good health by preparticipation history and physical examination performed at PERC, have no evidence of disease or disability that would impair performance of cycle ergometer exercise, and BMI < 95th percentile.

3. Provide the **inclusion and/or exclusion criteria** for the proposed subject population, as applicable.

[ ] Not applicable – This is not a clinical investigation and/or the characteristics of the population sufficiently describe the proposed subject population.

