**Exclusion criteria for Control Subjects**

- Regular use of anti-inflammatory medications parenterally, orally, or as inhaled agents.
- Regular use of bronchodilators
- Use of illegal drugs or abuse of alcohol
- Very high physical fitness (>55 ml O2/kg/min VO2max) or habitual physical activity, corresponding to an elite athlete training regimen
- Pregnancy or breastfeeding

4. If **exclusion** is based on age, gender, pregnancy/childbearing potential, social/ethnic group, or language spoken (e.g., Non-English Speakers), **provide a scientific rationale.**

This study will be limited to Children aged 8-17 years and Young Adults aged 18-35. The choice of studying young children/adolescents is due to the lack of information regarding the effect of acute bout of exercise and exercise training, in this specific age group on leukocyte function, genomic, and epigenetic responses. Few studies have been performed on adults looking at some aspects that we cover in this study, but results may not apply to children/adolescents, who present marked differences with adults. The young adults are going to serve as a reference group to those in 8-17 age bracket.

The effects of DXA to an unborn fetus, should a female subject be pregnant, are unknown, therefore pregnant individuals will be excluded.

To ensure protection of the subjects rights and safety, consent and assent forms will be carefully explained to them and to their authorized representatives. The study team has extensive experience in working with children and adults. It is also explicitly stated in the consent forms that participation in this protocol is voluntary.

An equal number of male and female participants will be included in the asthmatic and healthy groups. Different ethnic/racial groups will be included attempting to reproduce their respective distribution within the Orange County population, as per the latest report from the US Census Bureau. English and Spanish speaking subject will be recruited.

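### The primary gene-expression test is an unadjusted two-sample t-test that leaves out the sex, age and fitness factors on which controls are matched: valid, but an avoidable loss of some efficiency or protection

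*Protocol*

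**What the plan says.** **Primary analysis (protocol, Section 3B).** A change is computed for each subject and probe set. Probe sets that pass filtration and lie in "selected functional pathways will be examined for group difference using 2-sample t-test and further adjusted with false discovery rate (FDR) controlling adjustments". The word adjusted here refers to multiplicity. No covariate or pairing term is named.

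**Where covariates do appear.** For Aims 1 and 2 the only adjusted model is the secondary analysis of the secondary outcome (leukocyte cell function), a mixed model "adjusting for possible confounding factors such as gender, BMI percentile, and fitness level". Age is not listed there.

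**Matching (Sections 4A and 4B).** For the child groups, "we will recruit 70 asthmatics and 70 gender-, age- and fitness-matched controls"; adults are recruited likewise, 50 and 50. Section 4B repeats: "The control groups will be age, gender, and fitness matched with asthmatic participants". Table 2 recruits by sex and age stratum, for example "Mid and late pubertal boys (Tanner 3-5) age 8 - 17 years", and Section 4B adds: "An equal number of male and female participants will be included in the asthmatic and healthy groups".

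**Effect size (Section 4A).** "Our previous data showed that about 5% of the probe sets have an effect size over 0.9".

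**Medication.** The control exclusions in Section 4B include "Regular use of anti-inflammatory medications parenterally, orally, or as inhaled agents", and regular bronchodilator use. Section 3A lets asthma participants stay on their controller medication through the fast before the blood-draw challenge.

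**The concern.** The design and the primary analysis do not use the same information. Matching makes the groups alike on sex, age and fitness. A t-test that ignores those factors still counts the variation they explain as noise, so its standard error is too large when matching works. When matching or dropout leaves a difference in age or fitness among completers, the same test does nothing to correct it. These are alternatives, because the first assumes balance and the second assumes its absence. They should not be added together.

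The protocol also treats gender and fitness as worth adjusting for, but not in the result on which Aims 1 and 2 rest.

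A separate matter of interpretation is that Hypothesis 1 attributes abnormal leukocyte regulation to asthma without qualification, while regular anti-inflammatory or bronchodilator use can occur in the asthma group only.

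**Working it through.** **Inputs from the protocol.** Completers: about 60 per group (children) and 40 per group (adults). Two-sided two-sample t-test, FDR 0.05, 1000 to 2000 probe sets, about 5% with effect over 0.9 (all Section 4A). **Assumed:** R², the share of variance of the change explained by sex, age and fitness, shown from 0 to 0.3.

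**1. Reproduce Table 3.** With m probe sets examined and K to detect, per-test alpha = FDR × K × power / ((m − K) × (1 − FDR)), then noncentral-t power with 2n − 2 degrees of freedom. This reproduces all 48 cells to the printed decimal. For m = 1000, K = 50, 80% power, the computed effects are 0.899 (printed 0.9, 40 per group) and 0.727 (printed 0.7, 60 per group). The sample-size basis is therefore the same unadjusted test, and the stated power is met.

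**2. Per-test alpha in the protocol's own scenario.** Five per cent is 50 of 1000 or 100 of 2000. Both give 0.05 × 50 × 0.8 / (950 × 0.95) = 0.00222.

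**3. Adjusted test.** Three covariates leave 2n − 5 degrees of freedom, and the noncentrality is 0.9 × √(n/2) / √(1 − R²). For n = 40 and R² = 0.2 this is 4.025 / 0.894 = 4.50.

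**4. Comparator.** The t-test, simulated with identical covariates in both groups (effective matching).

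Power (%) at effect 0.9:

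| R² | 40/group, t-test | 40/group, adjusted | Gain | 60/group, t-test | 60/group, adjusted | Gain |
|---|---|---|---|---|---|---|
| 0 | 80.07 | 79.93 | -0.14 | 96.18 | 96.15 | -0.03 |
| 0.02 | 80.3 | 81.0 | 0.7 | 96.3 | 96.6 | 0.2 |
| 0.05 | 80.5 | 82.7 | 2.1 | 96.6 | 97.1 | 0.5 |
| 0.1 | 81.2 | 85.3 | 4.1 | 96.9 | 97.9 | 1.0 |
| 0.2 | 82.5 | 90.3 | 7.8 | 97.6 | 99.0 | 1.5 |
| 0.3 | 84.1 | 94.5 | 10.4 | 98.2 | 99.7 | 1.4 |

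Gains are taken before rounding. At effect 1.0 and the same alpha, 40 per group, the t-test has about 91, 92 and 93% at R² 0.1, 0.2 and 0.3, and the gain is about 2.5, 4 and 5 points.

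**5. Detectable effect at 80% power, R² 0.1 / 0.2 / 0.3.** 40 per group: 0.89 / 0.88 / 0.87 (t-test) against 0.85 / 0.81 / 0.75 (adjusted). 60 per group: 0.72 / 0.71 / 0.70 against 0.69 / 0.65 / 0.61.

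**6. Validity.** A full Benjamini-Hochberg simulation with balanced covariates (1000 independent probe sets, 50 with effect 0.9, 40 per group) gave a realised FDR of 2.9 / 1.3 / 0.6% for the t-test and 4.6 to 4.9% for the adjusted test. The t-test errs on the safe side when matching holds.

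**7. If balance fails.** For sex, random dropout from 70 to 60 or 50 to 40 per group leaves the difference in sex share within 4/60 = 0.067 (children) or 4/40 = 0.10 (adults) in about 97% of cases, so sex is well protected. For fitness, an assumed gap of 0.2 SD shifts the standardised difference by 0.2 × √R² = 0.06 / 0.09 / 0.11 at R² 0.1 / 0.2 / 0.3.

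**8. Medication.** No arithmetic applies. Regular users are excluded from one group and allowed in the other, so a between-group covariate cannot separate medication from disease. The protocol gives neither the share of users nor the size of any drug effect.

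**The case against.** The strongest reply is that nothing here is an error. The unadjusted test is valid, agrees with its own sample-size calculation and reaches the stated power. Keeping an adjusted model as secondary is a common choice. This stands, and the point is an improvement, not a correction of a wrong figure.

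The second reply is that the design already controls much of what adjustment would. Section 4A places the matched subjects below the 50th percentile of fitness norms, Table 2 limits children to Tanner 3-5, and Section 3A sets each subject's challenge work rate from his or her own threshold and peak VO2. Analysing within-subject change also removes stable differences in level. This stands too: R² may be small, and the lower rows of the table deserve as much weight as the upper ones. It does not settle the matter. No matching tolerance or pairing rule is stated for age or fitness, the formal eligibility lists give both groups only the same VO2max ceiling, and the age bands still span 8-17 and 18-35 years.

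Third, 0.9 is a floor for the top 5% of probe sets, not their typical effect, and larger effects shrink the gain. That is correct. The figure of about 10 points needs the highest assumed R², an effect of exactly 0.9, and the adult groups, which the protocol describes as a reference.

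A reader might infer that controller use at the blood draw goes unrecorded. The protocol does not support that: the data collection instruments are submitted separately and are not shown.

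**Conclusion.** The point holds in a limited form. The primary test leaves out factors that the design matches on and that, for gender and fitness, the same section calls possible confounders. With 40 per group, effect 0.9 and FDR 0.05, the gain from adjustment runs from about -0.1 points (R² = 0) through 0.5 to 2 (R² 0.02 to 0.05) to 4, 8 and 10 (R² 0.1, 0.2, 0.3). It is smaller for larger effects and at most about 1.5 points with 60 per group. R² is an assumption throughout. The power figures also assume balanced covariates and separate tests in children and adults, as the 60 and 40 per group suggest.

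A reader might infer that the primary result is biased or the trial underpowered. The documents support neither: the t-test is conservative under effective matching, Table 3 is reproduced in full, and imbalance is a possibility, not a stated feature.

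The medication point is a caveat on reading Aim 1. It cannot be sized from the protocol. A drug effect on the exercise response that is the same before and after training cancels in the training change, so Aim 2 is less affected.

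**What to change.** In Section 3B, before the data are seen, make the primary test for each probe set, separately in children and adults, the group term from a linear model of the change on group, sex, age (or Tanner stage in children) and baseline fitness. Apply Benjamini-Hochberg to those p-values and keep the two-sample t-test as a sensitivity analysis.

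The cost is a change of wording and three degrees of freedom: about 0.14 points of power at 40 per group and 0.03 at 60 if the covariates explain nothing. Sex, age, Tanner stage and peak VO2 are already collected. Table 3 can stay as it is.

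Separately, word the Aim 1 conclusion as applying to asthma as treated. No medication rule needs to change.
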